6.2.1 Ganetespib

Dose Level	Dose	Route	Schedule	Cycle Length
Starting dose	200 mg/m ²	IV	D1, 8, 15	28 days
First dose reduction	175 mg/m ²	IV	D1, 8, 15	28 days
Second dose reduction	150 mg/m ²	IV	D1, 8, 15	28 days

As detailed in Sections 5.1 and 14.2, at the time of initial study design, it was decided that in the case of more than 2 DLTs within the first 10 patients on Dose Level 1 (starting dose 200 mg/m²), the study would close temporarily to accrual while the events were adjudicated. Based upon results of this adjudication, the study would re-open at Dose Level -1 (starting dose 175 mg/m²). In this event, there would be only 1 allowed dose reduction (i.e. to 150 mg/m²) for patients entered at this starting dose level. Once decreased, doses would NOT be re-escalated. This DLT rule was not triggered for the first 10 patients randomized to Arm B; therefore enrollment to Arm B has continued at Arm B Dose Level 1 and treatment on Arm C has continued at Arm B Dose Level 1.

If possible, symptoms should be managed symptomatically. In the case of toxicity, appropriate medical treatment should be used (including anti-emetics, anti-diarrheals, etc.).

CONFIDENTIAL

This document is confidential. Do not disclose or use except as authorized.

All adverse events experienced by participants will be collected from the time of the first dose of study treatment, through the study and until the final study visit. Participants continuing to experience toxicity at the off study visit may be contacted for additional assessments until the toxicity has resolved or is deemed irreversible.

The following guidelines are provided for the modification of dose of ganetespib in the event of toxicities attributed by the investigator to this drug. Toxicities unrelated to ganetespib will not ordinarily result in modification of ganetespib dose.

Once a dose has been reduced, it should not be re-escalated.

Missed doses should be *skipped*, rather than held. Therefore, one cycle will nearly always be 4 weeks, allowing time for vacation, holidays, etc.

CONFIDENTIAL

This document is confidential. Do not disclose or use except as authorized.

Dose Modification Guidelines for Ganetespib

Toxicity	Grade	Guideline for management	Ganetespib dose modification*
Diarrhea	1	See Section 5.5	None

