	2	See Section 5.5	None; If unacceptable to patient or medically concerning despite maximal supportive measures, then skip until recovery to \leq grade 1 (or baseline), up to 21 days*. Restart at same dose**.
	≥ 3		If grade 3 or greater despite maximal supportive measures, skip until recovery to \leq grade 1 (or baseline), up to 21 days*. And then Reduce 1 dose level.
Nausea/vomiting	1 or 2	Treatment as appropriate.	None
	3 (First or 2 nd occurrence)	Treatment as appropriate.	Skip until recovery to \leq grade 1 (or baseline), up to 21 days*. And then Restart at same dose.
	3 (3 rd or more occurrence)		If grade 3 or higher despite optimal prophylactic measures, then skip until recovery to \leq grade 1 (or baseline), up to 21 days*. And then Reduce 1 dose level.
Fatigue	1	No intervention	None
	2	Treatment as appropriate.	None; If unacceptable to patient or medically concerning then hold until recovery to \leq grade 1 (or baseline), up to 21 days*. Restart at same dose**.
	3	Treatment as appropriate.	Skip until recovery to \leq grade 1 (or baseline), up to 21 days*. And then Reduce 1 dose level.
Other non-Hematologic toxicity	1	No Intervention	None
	2	Treatment as appropriate	None; If unacceptable to patient or medically concerning then skip until recovery to \leq grade 1 (or baseline), up to 21 days*. Restart at same dose**.
	2 prolonged or clinically significant and grade ≥ 3	Treatment as appropriate	Skip until recovery to \leq grade 1 (or baseline), up to 21 days And then Reduce 1 dose level*

CONFIDENTIAL

This document is confidential. Do not disclose or use except as authorized.

Toxicity	Grade	Guideline for management	Ganetespiib dose modification*
Infusion reactions	3	Treatment per institutional guidelines for infusion reactions	Contact Principal Investigator to determine whether patient may be retreated
	4	Stop infusion	Permanently discontinue
Thrombocytopenia	1 or 2	No intervention	None
	3	No intervention	Skip until recovery to \leq grade 1 (or baseline), up to 21 days And then Reduce 1 dose level*
Hemoglobin	1 or 2	Treatment as appropriate	None
	3	Treatment as appropriate	Skip until recovery to \leq grade 1 (or baseline), up to 21 days And then Reduce 1 dose level*
Neutropenia	1 or 2	No intervention	None
	3 (ANC < 1,000/ μ L) lasting > 7 days		Skip until recovery to \leq grade 1 (or baseline), up to 21 days And then Reduce 1 dose level*

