Cardiac toxicity	3 (first occurrence of QTc \geq 501 ms on average of triplicate recordings)		Reduce dose level to 120 mg/m ² after the QTc has decreased to at least < 470 ms.
	3 (repeat occurrence of QTc \geq 501 ms on average of triplicate recordings)		Permanently discontinue
	4 (QTc \geq 501 ms or > 60 ms change from baseline and torsades de pointes or polymorphic ventricular tachycardia or signs/symptoms of serious arrhythmia)		Permanently discontinue

* if no recovery after 21 days, patients should go off study

** if dose has been previously held for grade 2 toxicity and grade 2 symptoms recur, OR if the patient finds the symptoms unacceptable, hold dose until recovery to \leq grade 1 and then reduce dose one level

In the case of grade 4 hematologic or non-hematologic toxicity, ganetespiib should be skipped until recovery to grade 1 or less (or baseline), up to 21 days, and then the dose reduced to 150 mg/m². Subjects unable to tolerate ganetespiib at a dose level of 150 mg/m² or whose ganetespiib related toxicity has not returned to baseline or Grade \leq 1 within 21 days should stop ganetespiib. Patients may continue on fulvestrant alone at this time. Once permanently discontinued, ganetespiib should not be restarted.

In the case of a recurrent grade 3 event after prior dose reduction, ganetespiib should be held until the related toxicity has returned to baseline or Grade \leq 1. Subjects should be

CONFIDENTIAL

This document is confidential. Do not disclose or use except as authorized.

reduced by 1 additional dose level (i.e. 2 dose levels from baseline) upon restarting study drug. Only 2 dose reductions are allowed per protocol.

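### Section 6.2.1 gives two restart doses (175 and 150 mg/m²) after Grade 4 non-hematologic toxicity at the ganetespib starting dose, and its Grade 4 paragraph lacks exceptions that it needs

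*Combined protocol and SAP*

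**What the plan says.** Section 6.2.1 lists three ganetespib doses: 200 mg/m² at the start, then 175, then 150. It adds: "Once a dose has been reduced, it should not be re-escalated".

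The toxicity table that follows has three non-hematologic rows that matter here, each ending in a one-level reduction:

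- Diarrhea, graded ≥ 3: "If grade 3 or greater despite maximal supportive measures".
- Other non-hematologic toxicity: "2 prolonged or clinically significant and grade" ≥ 3.
- Nausea/vomiting, third or later occurrence: the grade column says 3, but the action text reads "If grade 3 or higher despite optimal prophylactic measures".

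Two Grade 4 rows, infusion reactions and QTc prolongation with serious arrhythmia, call for permanent discontinuation. A first average QTc of 501 ms or more without arrhythmia carries the instruction "Reduce dose level to 120 mg/m"², and Section 5.6.2 gives the same dose.

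The paragraph below the table covers all Grade 4 toxicity, hematologic or not. It says ganetespib "should be skipped until recovery to grade 1 or less (or baseline), up to 21 days, and then the dose reduced to 150" mg/m². It goes on to stop the drug for "Subjects unable to tolerate ganetespiib at a dose level of 150" mg/m². The next paragraph closes with "Only 2 dose reductions are allowed per protocol".

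**The concern.** Section 6.2 presents these as rules, and each should give one answer for one patient. Three places do not:

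- A patient with Grade 4 diarrhea at 200 mg/m² satisfies both the diarrhea row and the Grade 4 paragraph, which give different doses.
- The paragraph names no exceptions, although the same table sends some Grade 4 events to permanent discontinuation and some patients to a dose below 150.
- The 120 mg/m² dose is outside the dose-level list, and its relation to the cap of two reductions is not stated.

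At stake are consistent dosing across sites and safe restart after severe toxicity. Two sites could each follow the protocol and restart similar patients at different doses. The Nursing Protocol Education Sheet does not help, because it points staff to the two tables and does not mention the Grade 4 paragraph.

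**Working it through.** The plan states no figure to reproduce. The check traces each rule from each possible current dose, using the dose-level list, toxicity table and following paragraphs of Section 6.2.1.

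| Event | Current dose | Toxicity table | Grade 4 paragraph | Result |
|---|---|---|---|---|
| Grade 4 diarrhea despite maximal support, or other Grade 4 non-hematologic | 200 | 175 | 150 | Conflict |
| Same | 175 | 150 | 150 | Agree |
| Same | 150 | No lower listed level | 150, no change | Floor sentence points to stopping |
| Nausea/vomiting, third or later occurrence, if Grade 4 | 200 | 175 by the text; grade column says 3 | 150 | Lesser wording mismatch |
| Grade 4 infusion reaction | Any | Discontinue | 150 | Contradiction |
| Grade 4 QTc/arrhythmia | Any | Discontinue | 150 | Contradiction |
| Grade 4 non-QTc toxicity in a row covering Grade 4 | 120 | No lower listed level | 150 | An increase, barred by the no-re-escalation rule |
| First QTc ≥ 501 ms (Grade 3) | 200 | 120 | Not applicable | One reduction; within the cap |
| First QTc ≥ 501 ms (Grade 3) | 150, after two reductions | 120 | Not applicable | A third reduction; the cap is 2 |

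The fatigue, thrombocytopenia, hemoglobin and neutropenia rows stop at Grade 3. There the paragraph fills a gap and conflicts with nothing.

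**Size of the dose differences**

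- 200 to 175: 25/200 = 12.5%.
- 200 to 150: 50/200 = 25%.
- 200 to 120: 80/200 = 40%.
- 150 to 120: 30/150 = 20%.

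**Number of patients for the Grade 4 conflict.** The documents give no Grade 4 rate for single-agent ganetespib, so 1% to 5% is an assumption.

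- Arm B (n = 47): 0.01 × 47 = 0.47 and 0.05 × 47 = 2.35, or 0.5 to 2.4 patients.
- Including all 24 Arm A patients, should every one cross over to Arm C: 47 + 24 = 71; 0.01 × 71 = 0.71 and 0.05 × 71 = 3.55, or 0.7 to 3.6 patients.

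**Number of patients for the QTc case.** Section 2.1 (ECG Findings) reports prolonged QT as an adverse event in 7 of 580 treated patients: 7/580 = 1.2%. Applied to 71 patients, that is 71 × 7/580 = 0.86, before requiring 501 ms or more and two earlier reductions. The rate comes from adverse event reports, not systematic ECGs, so it is only a rough guide.

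**The case against.** The best defense is that the text below the table refines it. One paragraph deals with Grade 4 and the next with recurrent Grade 3. Several rows stop at Grade 3, so the Grade 4 paragraph is evidently the Grade 4 rule, and a specific instruction should prevail over a row graded ≥ 3. This is a natural reading, and 150 mg/m² is probably what was intended. But it does not settle the matter. If the paragraph always prevails, patients with Grade 4 infusion reactions or Grade 4 QTc/arrhythmia would restart at 150, against the table. If the table always prevails, Grade 4 diarrhea restarts at 175. Neither simple rule works for every row.

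Most of the defense of the 120 mg/m² dose stands:

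- Going from 200 to 120 is one reduction. It breaks neither the cap nor the 150 mg/m² floor, since that patient was never shown unable to tolerate 150.
- The table and Section 5.6.2 give the same dose, and Section 5.6.2 is permissive, so they do not contradict each other.
- A repeat QTc event is covered: permanent discontinuation.
- For other toxicity at 120, stopping is the sensible inference, since no lower level is listed and re-escalation is barred. It is not written down, though, and the Grade 4 paragraph read literally says otherwise.

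The nausea/vomiting row is also a weaker case. Its grade column says 3, and it applies only at the third or later occurrence despite optimal prophylaxis. Likewise, the diarrhea row applies only when maximal supportive measures have failed.

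**Conclusion.** The inconsistency is real and minor; the text is wrong as written. The 175 versus 150 conflict is confined to the 200 mg/m² dose and to the rows that reach Grade 4. The missing exceptions in the Grade 4 paragraph matter at least as much, because they concern events for which the table stops the drug. The clash with the reduction cap is confined to a first QTc of 501 ms or more after two earlier reductions.

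The headcount of 0.5 to 2.4 in Arm B, or 0.7 to 3.6 of up to 71, rests wholly on the assumed 1% to 5% rate. The documents do not support these stronger inferences that a reader might draw:

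- **That the problem is common because diarrhea is common.** The 79% in Section 2.1 counts diarrhea of any grade, and Section 5.5 describes managed diarrhea as generally mild to moderate.
- **That 31% is a ceiling.** That is the share of 378 pooled single-agent patients with a treatment-related event of Grade 3 or above. It does not bound the rate for this combination.
- **That the thorough QT study sizes the QTc problem.** Its 45 ganetespib-treated subjects were healthy men given a single dose.
- **That the 120 mg/m² dose is itself a breach of the floor or cap.** It is not, for the reasons given above.
- **That the trial's inference is affected.** No power, alpha or analysis figure depends on these rules.

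**What to change.** Three wording changes to Section 6.2.1:

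1. Limit the one-level-reduction rows for diarrhea, other non-hematologic toxicity and nausea/vomiting to Grade 3, in both the grade column and the action text. Prolonged or clinically significant Grade 2 stays in the other non-hematologic row. Grade 4 then follows the paragraph, at 150 mg/m², the more cautious of the two doses already in the text.
2. Add to the Grade 4 paragraph: *except where the table says permanently discontinue, and never above the current dose*. This is required, because the first change alone leaves the contradictions with the discontinuation rows and the 120 mg/m² dose.
3. Add 120 mg/m² to the dose-level list as a QTc-only level. State that ganetespib stops if a QTc reduction would be the third reduction, or if a further dose-reducing toxicity occurs at 120. The clinical team should confirm both stopping rules.

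The cost is a protocol wording amendment and a notice to sites. Sample size, visits and analysis do not change.

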6.2.2 Fulvestrant

Fulvestrant will be administered at a dose of 500 mg via intramuscular injection on Days 1 and 15 of Cycle 1, and then on Day 1 of each subsequent 28-day cycle.

There are no dose modifications of fulvestrant. Commercial supply fulvestrant will be administered in this study. The cost of fulvestrant will be billed to the patient and/or her insurance company.

If fulvestrant-related adverse events occur, they should be managed using standard clinical practice.

If grade 3 or 4 toxicity occurs that the treating investigator feels is related to fulvestrant, the study Principal Investigator should be contacted to discuss the case and determine whether continuation of protocol therapy is appropriate.

7. DRUG FORMULATION AND ADMINISTRATION

7.1 Ganetespib (STA-9090)

Refer to the Investigator's Brochure.

7.1.1 Description

Classification: HSP-90 inhibitor

Molecular formula: C₂₀H₂₀N₄O₃ **M.W.:** 364.40 g/mol

Physical description: white to off white powder

Ganetespib (STA-9090), chemical name *5-[2,4-dihydroxy-5-(1-methylethyl) phenyl]-2,4-dihydro-4-(1-methyl-1H-indol-5-yl)-3H-1,2,4-triazole-3-one*, is a novel triazolone heterocyclic compound. Its molecular formula is C₂₀H₂₀N₄O₃. STA-9090 is a white to off white powder with a molecular weight of 364.40 g/mol.

7.1.2 Form

Ganetespib 300mg/vial (25mg/mL)

Each vial contains 12mL of deliverable ganetespib (12.84mL total including an overage per USP requirements) at a concentration of 25 mg/mL in a PEG 300, polysorbate 80 and dehydrated alcohol cosolvent-surfactant system. The drug product is a colorless to slightly yellow, clear solution, essentially free of visible particles. The drug product vial can be identified with a dark blue cap and applicable label.

CONFIDENTIAL

This document is confidential. Do not disclose or use except as authorized.

Caution: Ensure that the ganetespib 300mg/vial (25mg/mL), is used with the instructions provided below. (Another drug product ganetespib 8 mg/mL is available that uses different instructions for preparation)

7.1.3 Storage and Stability

The Ganetespib 300mg/vial drug product should be stored at 20°C - 25°C (68°F – 77°F) with excursions allowed between 15°C and 30°C (59°F and 86°F) (USP Controlled Room Temperature). Alternatively, ganetespib may be store in a cool place between 8°C (46°F) and 20°C (68°F). DO NOT FREEZE.

7.1.4 Handling

Qualified personnel, familiar with procedures that minimize undue exposure to themselves and the environment, should undertake the preparation, handling, and safe disposal of the chemotherapeutic agent in a self-contained and protective environment.

7.1.5 Availability

Ganetespib is an investigational agent and will be supplied free-of-charge by Synta Pharmaceuticals.

7.1.6 Preparation

The dilution of ganetespib (STA-9090) (25 mg/mL) will be with D5W (5% Dextrose for Injection) to a concentration range of 0.1 mg/mL-1.1 mg/mL. Deviation from the proposed concentrations must be approved by the sponsor prior to administration. Infusion of the study drug must be completed within 4 hours once diluted with D5W.

Eligible subjects will receive ganetespib under the direction of a physician identified on the form FDA 1572. STA-9090 administration will be given over 60 minutes. The amount of ganetespib administered will be determined by the dose level to which the subject is assigned at study entry and by calculating the subject's body surface area (BSA).

Preparation Instructions for ganetespib 300mg/vial (25mg/mL) Infusion Solution

Study drug preparation should be performed under standard aseptic conditions following chemotherapeutic precautions.

In general, the following concentration range guidelines should be used when preparing ganetespib for infusion. Sponsor approved deviations from these recommendations may be necessary based on an individual subject's BSA and dose level. However, at no time should a concentration be outside the range of 0.1 - 1.1mg/mL. The target infusion volume should always be 500mL.

1. Calculate the total dose of ganetespib the subject is to receive based on their BSA:
$$\text{Total ganetespib dose (mg)} = \text{ganetespib dose (mg/m}^2\text{)} \times \text{BSA (m}^2\text{)}$$

2. Calculate the total volume of ganetespib drug product Solution (25mg/mL) needed:
Total ganetespib Solution (mL) = Total ganetespib dose (mg) from Step 1 / 25mg/mL
3. Calculate the total volume of 5% Dextrose for Injection (D5W) needed for preparation of the 500mL infusion solution:
Total D5W Volume (mL) = 500mL – Total ganetespib Solution (mL) from Step 2
4. Note: This step is required only for the Ganetespib 300/ml vial (25mg/ml) drug product if stored at 2°C-8°C.

Remove the appropriate number of ganetespib vials from the refrigerator and let them sit at ambient room temperature for approximately 20 minutes.

5. Into an empty 500mL, non-PVC, non-DEHP containing infusion bag or a 500mL glass bottle, transfer the calculated amount of D5W in Step 3 using a syringe and a needle. The D5W volume can also be adjusted to the calculated D5W volume in Step 3 if pre-filled bags/bottles are used.

Caution: Non-PVC, non-DEHP bags must be used.

6. Using a syringe and a 16G or 18G needle carefully withdraw the calculated amount of the ganetespib drug product solution from Step 2 and inject into the infusion bag containing D5W.

Note: Because of the viscosity of the drug product the 16G needle is recommended for ease of withdrawal.

7. Carefully squeeze the transfer ports, 4 corners of the bag, and the middle of the bag to ensure complete mixing of the drug product and D5W. Continue mixing by gently inverting the bag end-over-end 10 times. Visually inspect the final infusion solution. The final infusion solution should be clear and essentially free of any visible particles.

Caution: Do not use if a clear solution is not obtained. Contact the study Sponsor.

8. Attach the non-PVC, non-DEHP containing infusions set with a 0.22µm end-filter to the infusion bag.

Caution: Non-PVC, non-DEHP tubing with a 0.22µm filter must be used.

9. Store the infusion solution at room temperature until use avoiding direct exposure to light. Upon completing the infusion solution preparation, the one hour administration of the infusion solution must be completed within 4 hours. The time needed to prepare the dosing solution does not count against the 4 hour limit. There is no need to protect the IV bag from ambient light during the infusion.

Caution: Do not refrigerate the infusion solution.

Caution: The 1-hour infusion must be complete within 4 hours of completing the infusion solution preparation.

CONFIDENTIAL

This document is confidential. Do not disclose or use except as authorized.

7.1.7 Administration

1. Set up the infusion pump to deliver the 500mL ganetespiib infusion solution over 60 minutes

Note - Use of Vascular Access Devices:

Based on preclinical data, use of vascular access devices (VADs) (such as ports and peripherally-inserted central catheters [PICCS]) containing silicone catheters are permitted.

Use of VADs with catheters made of any other material is not allowed.

Following ganetespiib administration through a VAD, care should be taken to flush the line after each dose of study drug. Please follow routine clinical practice for care of patients utilizing VADs.

2. At the end of the infusion the IV tubing **must be flushed with D5W** to ensure complete delivery of the required dose of ganetespiib. The infusion rate of the D5W flush should be at the same rate as the drug infusion.
3. Dispose of used IV bags, tubing and used drug vials per institutional guidelines.

7.1.8 Ordering

Ganetespiib will be ordered and supplied by Synta Pharmaceuticals once the protocol is approved. Please refer to Appendix G: Section 4.0 for additional information.

7.1.9 Accountability

The investigator, or a responsible party designated by the investigator, must maintain a careful record of the inventory and disposition of the agent (investigational or free of charge) using the NCI Drug Accountability Record or another comparable drug accountability form. (See the CTEP website at <http://ctep.cancer.gov/protocolDevelopment> for the “Policy and Guidelines for Accountability and Storage of Investigational Agents” or to obtain a copy of the drug accountability form.)

7.1.10 Destruction and Return

At the end of the study, unused supplies of ganetespiib should be destroyed according to institutional policies. Destruction will be documented in the Drug Accountability Record Form.

7.1.11 Pharmacokinetics

The pharmacokinetics of STA-9090 administered at various doses to subjects with solid tumors on a weekly or twice-weekly schedule is under investigation in 2 Phase I trials.

CONFIDENTIAL

This document is confidential. Do not disclose or use except as authorized.

Preliminary data and calculated parameters are available in subjects with solid tumors for doses up to 259 mg/m². C_{max} and AUC increase in approximate proportion to dose irrespective of dosing day with virtually identical dose-exposure ratios for Day 1 and Day 15, indicating linear pharmacokinetics and a lack of drug accumulation. Distribution and elimination phases of STA-9090 show maximum concentration at the end of the infusion declining by approximately 10-fold within the first hour and nearly 100-fold within 10 hours following infusion termination. Mean terminal half-lives have ranged from approximately 5.2 to 14 hours. STA-9090 plasma concentrations on Day 1 and 15 are comparable following either once or twice weekly dosing, indicating the lack of drug accumulation.

